We will also measure structure of care variables. These include patient use of consistent PCP care, home health services, and patient insurance. Clinic characteristics are size, support staff number, proportion of Medicare and Medicaid patients. Several baseline variables relate to diabetes but because they are also outcome variables they will be described later. As shown in table 1, many of these baseline and control variables are measured in the EHR and Epic administrative reports, or by claims. Some are measured by validated survey instruments, which are discussed briefly below.

We will collect many process of care measures at baseline and at follow-up. These include: a) provider use of Epic templates and tools; b) provider attendance at educational sessions; c) PM-PCP communication; d) PM-caregiver contact frequency; e) referral for caregiver-support services; f) cognitive screening of diabetes patients over 75; g) change in diabetes medications; h) change in hypertensive medications; i) change in anticholinergic burden; j) change in medication complexity. These variables are measured by EHR review and Epic administrative systems.

Outcome variables include HbA1c level and blood pressure. These variables will be measured at 0, 6, 12 and 24 months when available. Our main outcome is the proportion of patients achieving consensus HbA1c targets. BP will be measured by proportion of patients achieving consensus BP targets per our guideline. These variables will be measured by the EHR.

Utilization outcome variables are ED, hospital, SNF and ambulatory clinic utilization measured by EHR and by claims (for non-New York Langone Health utilization). SNF days must be measured by claims; Epic reports have discharge destination but do not have SNF days. Utilization variables will be measured at 6, 12, 24 months; the baseline measures include a 20 month look back at utilization.

Multiple caregiver reported outcomes about the caregiver and about the patients will also be

collected at 0, 6, 12, 24 months. General outcomes include: a) caregiver perception of care quality (our main caregiver-reported outcome), dyad care goals, preferences, and satisfaction; b) treatment burden; c) caregiver global health. Dementia and diabetes specific outcomes include: a) patient dementia symptoms; b) caregiver diabetes stress.

Below is a brief description of the instruments we will use, all of which have been studied and validated, although not always with caregivers.

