## 7. Data Analysis

We will begin all analyses with descriptive summary statistics and graphical displays of all variables. Continuous variables will be summarized with means, medians, standard deviation and interquartile range; categorical variables will be summarized with frequencies. We will assess the balance by treatment assignment of patients in the INT and CON clinics with respect to demographic and clinical characteristics (e.g., age, gender, Charlson Index, socioeconomic status, baseline TBQ, etc.) using standard tests (t-tests, Wilcoxon rank-sum tests, and  $\chi^2$  tests as appropriate). Any factors that appear to be unbalanced by treatment assignment will be considered as adjustment factors in the primary analyses. All hypothesis testing will be two-sided and conducted using a significance level of 0.05.

The primary outcome of 'on target' HbA1C values will be measured for each patient as a binary indicator. The primary analysis will use a generalized linear mixed model approach, with a logit link, for the probability of being 'on target.' The treatment group (CON vs INT) will be the primary fixed effect of interest; we will also include the practice as a random effect to accommodate clustering of patients within clinics. We will also explore non-parametric methods such as quantile regression or other rank-based approaches. As noted above, randomization should obviate the need for any additional covariate adjustment, but we will explore whether adjustment for clinic-level characteristics (e.g., clinic size) and provider-level characteristics (e.g., provider demographics and panel size) is necessary. We will use standard assessments of goodness-of-fit, including residual plots, to evaluate the models. Finally, in addition to reporting the treatment difference in terms of the odds ratio from the logistic regression, we will report absolute risk difference as well.

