All clinical trials are at risk for missing data. Although we will attempt to retain as high a fraction of participants as possible, we acknowledge that some attrition is likely, leading to missing outcome values. The generalized linear mixed models proposed for the primary and secondary analyses incorporate an assumption of data that are missing at random (MAR), meaning that the likelihood of a value being missing depends on observable characteristics (e.g., sex, age, baseline clinical status, etc). In sensitivity analyses, we will assess the impact of different assumptions about the missing data mechanism, and will determine the robustness of trial results to these different assumptions. These sensitivity analyses will take the several forms. The first extreme value imputation, in which we assume that all members of one intervention group experience either a success or a failure (e.g., HbA1 on or off target) while the opposite occurs in the other intervention group. We will also apply a more formalized assessment using the Index of Sensitivity to Nonignorability, developed by [name] and colleagues, which provides an objective assessment of the robustness of trial results to different assumptions about the missing data mechanism.

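### The missing-data assumption stated for the primary HbA1c model is broader than the model as specified supports, so missingness whose pattern differs by arm can bias the comparison

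*Combined protocol and SAP*

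**What the plan says.** All of this is in Section 7 (Data Analysis) unless noted.

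- **Outcome.** "The primary outcome of 'on target' HbA1C values will be measured for each patient as a binary indicator". No primary time point is named there.
- **Model.** A logistic mixed model. "The treatment group (CON vs INT) will be the primary fixed effect of interest", and "we will also include the practice as a random effect to accommodate clustering of patients within clinics".
- **Covariates.** The default is that "randomization should obviate the need for any additional covariate adjustment". Two optional routes exist. The first is "Any factors that appear to be unbalanced by treatment assignment will be considered as adjustment factors in the primary analyses". The second is in the paragraph on the treatment burden score (TBQ), which says that the need for demographic or clinical adjustment will be assessed, as for the primary outcome. Clinic-level and provider-level factors will also be explored.
- **Missing data.** Attrition is called likely, and the models are said to assume missing at random, "meaning that the likelihood of a value being missing depends on observable characteristics (e.g., sex, age, baseline clinical status, etc". Sensitivity analyses are extreme-value imputation and the Index of Sensitivity to Nonignorability.
- **Repeated measures.** Longitudinal mixed models are described for treatment burden and the Dementia Severity Rating Scale (DSRS), not for HbA1c.
- **Data source.** Section 5.4 (Measures) takes HbA1c and blood pressure from the health record: "These variables will be measured at 0, 6, 12 and 24 months when available".

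**The concern.** A likelihood-based mixed model gives valid results under missing at random only with respect to what it contains. With one outcome per patient there is no earlier value of the same patient to carry information, and with no baseline terms there is nothing else. A missing indicator simply leaves the likelihood. What is fitted is an analysis of patients with a value, assured of validity only if missingness is unrelated to outcome given arm and clinic. That is a stronger condition than the one the plan states.

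The condition is open to doubt here. An HbA1c exists only if the patient has had one taken in care. Under Section 4 (INT Clinics, PM Activities), panel managers in the intervention arm help bring about primary care visits; control clinics have no panel manager. So which patients have a follow-up value may differ by arm. If control clinics lose sight of poorly controlled patients and intervention clinics keep them, the control patients who remain look better controlled and a benefit is understated. The reverse pattern would manufacture a benefit.

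**Working it through.** **No planned figure to reproduce.** The documents give no attrition rate, on-target rate or intraclass correlation. The inputs below are assumptions, chosen to show a range.

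**Closed form, no true effect.** Let half the patients be on target at baseline. Let p_on and p_off be the follow-up on-target proportions by baseline status, the same in both arms, and m_on and m_off the missing proportions in an arm. Among patients with a value,

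P = [0.5(1 - m_on) p_on + 0.5(1 - m_off) p_off] / [0.5(1 - m_on) + 0.5(1 - m_off)].

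First row: control = (0.45 × 0.8 + 0.30 × 0.3)/0.75 = 0.450/0.75 = 0.600; intervention = (0.45 × 0.8 + 0.425 × 0.3)/0.875 = 0.4875/0.875 = 0.557. The true value is 0.55 in both arms.

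| Missing on/off, CON | Missing on/off, INT | p_on / p_off | CON | INT | INT - CON |
|---|---|---|---|---|---|
| 10% / 40% | 10% / 15% | 80% / 30% | 60.0% | 55.7% | -4.3 points |
| 10% / 40% | 10% / 15% | 60% / 40% | 52.0% | 50.3% | -1.7 points |
| 10% / 30% | 10% / 20% | 80% / 30% | 58.1% | 56.5% | -1.7 points (0.5647 - 0.5813) |
| 10% / 30% | 10% / 20% | 60% / 40% | 51.3% | 50.6% | -0.7 points (0.5059 - 0.5125) |

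**When there is no bias.** With p_on/p_off of 70%/30%, missingness of 10%/30% in both arms gives a difference of 0.000 and an odds ratio of 1.00. So does missingness of 10% in one arm and 30% in the other, unrelated to baseline status.

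**The sign can turn.** With 70%/30%, missing 10%/30% in the intervention arm and 30%/10% in control: 0.42/0.80 - 0.38/0.80 = 0.525 - 0.475 = +5.0 points, odds ratio 1.22, with 20% missing in each arm.

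**Simulation of the planned model.** About 1,000 patients, no true effect, clinic standard deviation 0.25 on the logit scale (assumed), 70%/30% on target, 400 runs per setting. Section 3.1 gives 20 practices but 9 + 9 = 18 by arm, so both were run. The nominal level follows the plan: "All hypothesis testing will be two-sided and conducted using a significance level of 0.05".

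| Missing pattern (good/poor baseline) | Arm + clinic: odds ratio (18 / 20 clinics) | Rejection | With baseline status added: odds ratio | Rejection |
|---|---|---|---|---|
| 10/30 in both arms | 1.00 / 1.00 | 7.0% / 5.8% | 1.00 / 1.00 | 7.0% / 5.0% |
| INT 10/30, CON 20/20 | 1.10 / 1.10 | 9.2% / 12.2% | 0.99 / 0.99 | 7.2% / 7.2% |
| INT 10/30, CON 30/10 | 1.20 / 1.21 | 19.5% / 19.8% | 0.98 / 0.99 | 6.2% / 7.0% |

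Monte Carlo error on the rejection rates is about 1 to 2 points.

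**Does the imbalance trigger catch it?** A balance test on all enrolled patients flagged the baseline predictor in only 3% to 7% of runs. It is balanced at enrolment and becomes unbalanced only among patients with a value.

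**Do the sensitivity analyses supply the missing estimate?** With 20% missing per arm and 50% on target, extreme-value imputation runs from 0.40 - 0.60 = -0.20 to 0.60 - 0.40 = +0.20. That is too wide to settle a bias of 1 to 5 points. The nonignorability index measures sensitivity to departures from ignorable missingness; it is not an estimate that uses age, sex or baseline status.

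**The case against.** The strongest reply is that the plan declares an assumption, follows it with sensitivity analyses, and leaves room for covariates. Several parts of that stand.

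- Arm and clinic only is the default, not an absolute. Section 7 has a second adjustment route that does not depend on imbalance. But it turns on an undefined need for adjustment and names neither variables nor a link to missingness, so it does not make the model match the assumption.
- HbA1c comes from the health record. A dyad that stops answering surveys may still have a value, so survey attrition does not measure missing outcomes.
- Table 1 describes the HbA1c outcome as a proportional change, with values at baseline and three later waves, so baseline status might enter in a way not spelled out. One indicator per patient is still the natural reading of Section 7.
- The size depends on how strongly baseline status predicts follow-up. Moving from 80%/30% to 60%/40% cuts the difference by more than half.

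A reader might infer that attrition will bias the HbA1c result, or that more missing values in one arm is enough to do so. The documents do not support either. Bias under the null needs missingness to be related to outcome-predictive factors differently by arm, and no attrition data are given from which to judge that.

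**Conclusion.** The mismatch is real: the stated assumption conditions on characteristics that the default primary model does not contain, and nothing else planned supplies an estimate that does. The consequence is conditional. If the relation between baseline status and having an HbA1c differs by arm, the comparison can be biased in either direction; the panel managers' role makes such a difference plausible but does not establish it. The illustrated sizes, -0.7 to -4.3 points and +5.0 points under a reversed pattern, rest wholly on assumed inputs. The plan gives no target effect against which to call them large or small. This is an inexpensive improvement that should be made, not a flaw that invalidates the design.

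**What to change.** Keep the arm-plus-practice logistic model and its estimand, but fit it after multiple imputation of missing HbA1c status. Impute by arm and account for clinic. Use variables already listed in Table 1: baseline HbA1c (itself imputed where missing), age, sex, Charlson index, baseline DSRS, and HbA1c at other waves. State which wave is imputed as the primary outcome. Keep the two planned sensitivity analyses for departures from missing at random.

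A simpler alternative is to prespecify baseline HbA1c status, age, sex and Charlson index as covariates and report a risk difference standardised to all enrolled patients. The odds ratio is then conditional on those covariates, HbA1c from later waves is not used, and missing baseline HbA1c still needs handling.

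A longitudinal logistic model with patient random effects is not a like-for-like substitute. Its odds ratio is conditional on the patient, and Section 7 does not set out such a random-effects structure even for the secondary outcomes.

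In either case, report the proportion of patients with an HbA1c at each wave by arm.

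The cost is SAP wording and modest programming, with no new data. The downside is an imputation model to specify and check. The choice should be fixed before outcome data are reviewed.

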## **8. Data and Safety Monitoring**

This study will be monitored by **1) the multiple Principle Investigators (mPIs) and 2) the Data Safety Monitoring Board (DSMB).**

### **8.1 mPI responsibilities:**

- Provide oversight of daily operations and on-site monitoring of data accuracy and quality, adherence to the research design, methods and procedures outlined in the protocol
- Monitor AE and SAE and follow-protocols for those events outlined in Section 10, including reporting these events to the IRB and DSMB.

### **8.2 DSMB responsibilities:**

- Review the research protocol, informed consent documents and plans for data safety and monitoring;
- Advise the NIA on the readiness of the study staff to initiate recruitment;
- Evaluate the progress of the trial, including periodic assessments of data quality and timeliness, recruitment, accrual and retention, participant risk versus benefit, performance of the trial sites, and other factors that can affect study outcome;
- Consider factors external to the study when relevant information becomes available, such as scientific or therapeutic developments that may have an impact on the safety of the participants, and outcomes or ethics of the trial;
- Review study performance, make recommendations and assist in the resolution of problems reported by the mPrincipal Investigators;
- Protect the safety of the study participants;
- Report to NIA on the safety and progress of the trial;

- Make recommendations to the NIA and to the Multiple Principal Investigators concerning continuation, termination or other modifications of the trial based on the observed beneficial or adverse effects of the treatment under study;
- Review interim analyses to assess study recruitment and outcome milestones which are clearly defined in advance of data analysis and have the approval of the DSMB;
- Ensure the confidentiality of the study data and the results of monitoring; and,
- Assist the NIA by commenting on any problems with study conduct, enrollment, sample size and/or data collection.

There will also be a data monitoring committee consisting of the statistician, [name], a DataCore representative, and Co-I [name]. This committee will meet twice yearly during the first three years of the trial to review the survey data and any data to be presented to the DSMB. In the last year, when utilization information from the EHR and claims are becoming available, this group will meet every two months.

## **9. Ethics/Protection of Human Subjects**

### **9.1 Ethical Standards**

The investigator will ensure that this study is conducted in full conformity with Regulations for the Protection of Human Subjects of Research codified in 45 CFR Part 46.

### **9.2 Institutional Review Board**

The protocol, informed consent form(s), recruitment materials, and all participant materials will be submitted to the IRB for review and approval. Approval of both the protocol and the consent form must be obtained before any participant is enrolled. Any amendment to the protocol will require review and approval by the IRB before the changes are implemented to the study. All changes to the consent form will be IRB approved; a determination will be made regarding whether previously consented participants need to be re-consented.

## **10. Data Handling and Record Keeping**

### **10.1 Data Storage and Management Responsibilities**

All study personnel will be trained in data confidentiality, Human Subjects Research and HIPPA compliance. Data will be stored using HIPAA-compliant REDCap electronic database hosted at NYU Langone Health. To protect against risk to loss of subject confidentiality, all records exported from REDCap will be coded with anonymous identifiers. Only de-identified data will be shared with the research team without a need to know identifying information. Documentation of consent will be encrypted and will not be known by the PM and clinical team. Data will be compiled from all of the subjects in the study and aggregated for analysis and publication. All identifying data will be eliminated from files before the statistician analyzes the data. All electronic data will be kept in password-protected databases and program files. Procedures for maintaining confidentiality will be reviewed quarterly with the research team to assure compliance. Audiotaped intervention sessions that will be used to ensure the quality of the intervention and judge treatment fidelity will be reviewed by [name] and subsequently destroyed.

NYULH has privacy provisions that are strictly adhered to, including mandatory Security Awareness and HIPAA training of all employees from custodial staff to Administration; mandatory training for all clinical trials staff, which includes Protection of Human Subjects training. All staff must sign a confidentiality agreement upon employment, and NYULH meets or exceeds all HIPAA requirements. These requirements pertain both to our study personnel and to any MCIT or data management personnel who come into contact with our databases, which are stored on NYULH IT secure servers.

All resources, including web, database, and file servers, are protected from outside intrusion by a firewall that blocks unauthorized access to the LAN by any unauthorized user originating from the Internet by using a sophisticated combination of secure application proxies and packet filtering. Internal network security is maintained through Active Directory authentication. Intrusion detection software is employed to scan for attempted break-ins. User IDs and passwords are assigned and controlled as per SOP "SD004: Study Security", and users are required by the system to change their passwords regularly. Access to clinical trials or other sensitive data is strictly limited and is granted only by the Director of the Technical Support Unit.

## **10.2 Study Record Retention**

In compliance with NIH policy, study records will be retained for a minimum of 3 years after study completion.

## **10.3 Publication and Data Sharing Policy**

This study will comply with the NIH Public Access Policy, which ensures that the public has access to the published results of NIH funded research. It requires scientists to submit final peer-reviewed journal manuscripts that arise from NIH funds to the digital archive PubMed Central upon acceptance for publication.

## **12. Study Finances**

### **12.1 Funding Source**

This study is financed through a grant from the National Institute on Aging (NIA).

### **12.2 Costs to Subjects**

There are no costs for participation.

### **12.3 Payment for Participation**

Caregivers will be provided a \$20 gift card upon completion of each of the 4 surveys (baseline, 6 months, 12 months and 24 months) and an additional \$20 gift card should they complete a qualitative interview.

